Table 10-1 Study Drug..... 38

Table 11-1 Safety Laboratory Test Panels 43

Table 11-2 Acceptable Methods of Contraception..... 46

Table 13-1 Grading of AE Severity 51

Table 13-2 Classifications for AE Causality..... 52

Table 13-3 Classifications for Study Drug Action Taken With Regard to an AE 52

Table 13-4 Classifications for Outcome of an AE 53

List of Figures

Figure 2-1 VX19-445-117 Study Design 6

Figure 9-1 VX19-445-117 Study Design 29

List of Abbreviations

Abbreviation	Definition
ADL	activities of daily living
AEs	adverse events
ALP	alkaline phosphatase
ALT	alanine transaminase
AST	Aspartate transaminase
β	beta, apparent elimination rate constant
BMI	body mass index
CD	compact disc
CF	Cystic Fibrosis
CFRD	CF related diabetes
CFTR	CF transmembrane conductance regulator protein
CFTR	CF transmembrane conductance regulator gene
CGM	continuous glucose monitoring
CI	confidence interval
CRF	case report form
CRP	C-reactive protein
CSR	clinical study report
CTCAE	Common Terminology Criteria for Adverse Events
CYP	cytochrome P450
ECG	electrocardiogram
EDC	electronic data capture
EENT	eyes, ears, nose, and throat
ELX	elexacaftor
ETT	Early Termination of Treatment
EU	European Union
F/MF	F508del mutation and a minimal function mutation
F508del	CFTR gene mutation with an in-frame deletion of a phenylalanine codon corresponding to position 508 of the wild-type protein
FAS	Full Analysis Set
FDA	Food and Drug Administration
FDC	fixed-dose combination
FE-1	fecal elastase-1
FEF _{25%-75%}	forced expiratory flow, midexpiratory phase
FEV ₁	forced expiratory volume in 1 second
FSH	follicle-stimulating hormone
FVC	Forced vital capacity
GCP	Good Clinical Practice
GGT	gamma-glutamyl transferase
GIP	glucose-dependent insulintropic polypeptide
GLI	Global Lung Function Initiative
GLP-1	glucagon-like peptide 1
GPP3	Good Publication Practices

Abbreviation	Definition
GPS	Global Patient Safety
HbA1c	hemoglobin A1c
HIPAA	Health Insurance Portability and Accountability Act
ICF	informed consent form
ICH	International Council for Harmonization
ICMJE	International Committee of Medical Journal Editors
IEC	independent ethics committee
IGT	impaired glucose tolerance
IMP	investigational medicinal product
IND	Investigational New Drug (application) (US)
IRB	institutional review board
IRT	immunoreactive trypsinogen
IVA	ivacaftor
IWRS	interactive web response system
LS	least squares
LUM	lumacaftor
MAGE	maximum amplitude of glucose excursions
max	maximum value
min	minimum value
MMRM	mixed-effects model for repeated measures
n	size of subsample
N	total sample size (e.g., number of subjects treated)
NGT	normal glucose tolerance
OATP1B1	organic anion transporting polypeptide 1B1
OATP1B3	organic anion transporting polypeptide 1B3
OGTT	oral glucose tolerance test
P	probability
PC	publication committee
PD	pharmacodynamic
PEs	physical examinations
P-gp	P-glycoprotein
PIs	principal investigators
ppFEV ₁	percent predicted forced expiratory volume in 1 second
q12h	every 12 hours
qd	once daily
QTcF	QT interval corrected by Fridericia's formula
SAE	serious adverse event
SAP	Statistical Analysis Plan
SC	steering committee
SD	standard deviation
SET	Study Execution Team
SUSARs	suspected, unexpected, serious adverse events
SwCl	sweat chloride

Abbreviation	Definition
TE	Treatment-emergent
TEAEs	treatment emergent adverse events
TEZ	tezacaftor
t -test	statistical test used when the independent variable is binary and the dependent variable is continuous
ULN	upper limit of normal
US	United States
USA	United States of America
WHO-DD	World Health Organization-Drug Dictionary

5 INTRODUCTION

5.1 Background

Cystic fibrosis (CF) is an autosomal recessive genetic disease with serious morbidities and frequent premature mortality. CF affects more than 70,000 individuals worldwide¹ (approximately 31,000 in the US² and 48,000 in the EU³).

CF is caused by decreased quantity and/or function of the CFTR protein due to mutations in the *CFTR* gene.⁴ CFTR is a channel that regulates the flow of chloride and other anions across epithelia in multiple organs and tissues, including the lungs, pancreas and other gastrointestinal organs, and sweat glands.⁵ Despite progress in the treatment of CF with antibiotics and mucolytics, the current median age at death among people with CF is approximately 30 years, and the predicted median age of survival is approximately 47 years.^{2,3} More effective treatments are needed for CF.

The most common disease-causing mutation is *F508del*: approximately 84.7% of people with CF in the US and 81.1% in Europe have at least one *F508del* allele.^{2,3}

At present CF does not have a cure. CFTR modulators (i.e., correctors and potentiators) represent a major advancement in the treatment of CF because they are systemic therapies that target the underlying cause of the disease and have been shown to improve CF survival by modifying the course of disease.^{6,7} The clinical testing and regulatory approval of CFTR modulators in certain countries for the treatment of people with CF caused by specific *CFTR* genotypes has established the therapeutic value of specific regimens developed by Vertex. These treatment regimens include ivacaftor (IVA) monotherapy (Kalydeco™), lumacaftor (LUM)/IVA dual combination therapy (Orkambi™), tezacaftor (TEZ)/IVA dual combination therapy (Symdeko™, Symkevi™) and elxacaftor (ELX)/TEZ/IVA triple combination therapy.

The ELX/TEZ/IVA regimen is the first medicine to demonstrate clinical benefit in patients with a single *F508del* allele, regardless of the mutation of the second allele. A pivotal Phase 3 program in CF subjects 12 years of age or older demonstrated that ELX/TEZ/IVA provides substantial improvements in lung function, CFTR function, and nutritional status, and was generally safe and well tolerated with a low rate of treatment discontinuation.

5.2 Study Rationale

Abnormal glucose metabolism is a common complication from CF, and CF-related diabetes (CFRD) reaches a prevalence of approximately 50% of adults overall and approximately 80% of adults with a severe genotype (i.e., heterozygous for *F508del* and a minimal function mutation [F/MF])⁸. The primary deficiency is one of impaired insulin secretion due to loss of pancreatic beta cell (insulin producing) mass and function. Multiple mechanisms contribute to pancreatic destruction, including impaired bicarbonate/fluid secretion and thickened mucus (mucoviscidosis), which blocks exocrine ducts and results in fatty/fibrotic replacement of the majority of the pancreas. Over time, inflammation is believed to further impair the function of reduced endocrine islet cell mass and function. Genetics and other as yet unknown mechanisms are also believed to play a role in the progression to CFRD, and the need for exogenous insulin treatment, which is currently the standard of care. Patients who develop impaired glucose tolerance (IGT) or CFRD are known to have faster decline in lung function, higher mortality, and overall significantly increased burden of disease⁸. The present study is designed to evaluate the

effect of ELX/TEZ/IVA on impaired glucose homeostasis in CF subjects with abnormal glucose metabolism.

6 STUDY OBJECTIVES

6.1 Primary Objective

To evaluate the effect of ELX/TEZ/IVA on glucose tolerance in CF subjects with IGT or CFRD

6.2 Secondary Objective

To evaluate the safety and tolerability of ELX/TEZ/IVA

7 STUDY ENDPOINTS

7.1 Primary Endpoint

Change from baseline in 2-hour blood glucose levels following an oral glucose tolerance test (OGTT) to the average of Week 36 and Week 48

7.2 Secondary Endpoints

- Proportion of subjects with improvement in dysglycemia categorization (CFRD, IGT, normal glucose tolerance [NGT]) at Week 48
- Safety and tolerability of ELX/TEZ/IVA based on adverse events (AEs), clinical laboratory values, ECGs, vital signs, and pulse oximetry

7.3 Other Endpoints

- Change from baseline in sweat chloride (SwCl) through Week 48
- Absolute change in body mass index (BMI) from baseline at Week 48
- Absolute change in body weight from baseline at Week 48
- Change from baseline in hemoglobin A1c (HbA1c) and fructosamine at Week 48
- Change from baseline in insulin use (dose) at Week 48 in subjects using insulin
- Change from baseline in post-OGTT diabetes-related biomarkers (including insulin, C-peptide, glucagon, calculated indices of insulin secretion [insulinogenic index], and insulin resistance [HOMA-IR]) at Week 48
- Change from baseline in biomarkers of inflammation (including C-reactive protein [CRP]) at Week 48
- Change from baseline in biomarkers of pancreatic function (including fecal elastase-1 [FE-1] and serum immunoreactive trypsinogen [IRT]) at Week 48
- Change from baseline in post-OGTT incretin levels (including glucagon-like peptide 1 [GLP-1] and glucose-dependent insulinotropic polypeptide [GIP]) at Week 48
- Change from baseline in percent of time spent in target blood glucose range of ≥ 70 to < 140 mg/dL (≥ 3.89 to < 7.77 mmol/L) as measured by 7-day continuous glucose monitoring (CGM) in subjects with CFRD at Week 48
- Change from baseline in selected CGM parameters (including but not limited to percent of time spent between ≥ 140 and < 200 mg/dL [≥ 7.77 and < 11.10 mmol/L], percent of time

spent ≥ 200 mg/dL [≥ 11.10 mmol/L], and maximum amplitude of glucose excursions [MAGE]) in subjects with CFRD at Week 48

8 STUDY POPULATION

Eligibility will be reviewed and documented by an appropriately qualified member of the investigator's team before subjects are enrolled.

Subjects who meet all of the inclusion criteria and none of the exclusion criteria will be eligible.

8.1 Inclusion Criteria

1. Subject (or his or her legally appointed and authorized representative) will sign and date an informed consent form (ICF), and, when appropriate, an assent form.
2. Willing and able to comply with scheduled visits, treatment plan, study restrictions, laboratory tests, contraceptive guidelines, and other study procedures.
3. Subjects (male and female) 12 years of age or older on the date of informed consent.
4. Subjects heterozygous for *F508del* and an MF mutation (F/MF genotypes, see [Appendix A](#) for definition and non-exhaustive list of eligible MF mutations).
 - a. Genotype should be confirmed at the Screening Visit.
 - b. If the screening *CFTR* genotype result is not received before the first dose of study drug, a previous *CFTR* genotype laboratory report may be used to establish eligibility.
 - c. Subjects who have been enrolled and whose screening genotype does not confirm study eligibility must be discontinued from the study (Section 9.9).
5. Forced expiratory volume in 1 second (FEV₁) value $\geq 30\%$ of predicted mean for age, sex, and height (equations of the Global Lung Function Initiative [GLI])⁹ at the Screening Visit (spirometry measurements must meet American Thoracic Society/European Respiratory Society criteria¹⁰ for acceptability and repeatability) and stable CF disease as judged by the investigator.
6. Willing to remain on a stable CF treatment regimen (other than *CFTR* modulators) through completion of study participation.
7. Abnormal glucose tolerance as determined by an OGTT, classified as either IGT (defined as 2-hour post-OGTT blood glucose level ≥ 140 to < 200 mg/dL [≥ 7.77 to < 11.10 mmol/L]) or CFRD (defined as either fasting hyperglycemia [blood glucose level ≥ 126 mg/dL (≥ 7.00 mmol/L) after an 8-hour fast] or 2-hour post-OGTT blood glucose level ≥ 200 mg/dL [≥ 11.10 mmol/L]).

8.2 Exclusion Criteria

1. History of any illness or any clinical condition that, in the opinion of the investigator, might confound the results of the study or pose an additional risk in administering study drug(s) to the subject. This includes, but is not limited to, the following:
 - Clinically significant liver cirrhosis with or without portal hypertension
 - Solid organ or hematological transplantation

[figure not shown]
- Alcohol or drug abuse in the past year, including, but not limited to, cannabis, cocaine, and opiates, as deemed by the investigator
 - Cancer, except for squamous cell skin cancer, basal cell skin cancer, and Stage 0 cervical carcinoma in situ (all 3 with no recurrence for the last 5 years)
2. Type 1 or Type 2 diabetes.
 3. Duration of CFRD ≥ 5 years.
 4. Any clinically significant laboratory abnormalities at the Screening Visit that would interfere with the study assessments or pose an undue risk for the subject (as deemed by the investigator).
 5. Any of the following abnormal laboratory values at screening:
 - Hemoglobin < 10 g/dL
 - Total bilirubin $\geq 2 \times$ upper limit of normal (ULN)
 - Aspartate transaminase (AST), alanine transaminase (ALT), gamma-glutamyl transferase (GGT), or alkaline phosphatase (ALP) $\geq 3 \times$ ULN
 - Abnormal renal function defined as glomerular filtration rate ≤ 50 mL/min/1.73 m² (calculated by the Modification of Diet in Renal Disease Study Equation)^{11, 12} for subjects ≥ 18 years of age and ≤ 45 mL/min/1.73 m² (calculated by the Counahan-Barratt equation)¹³ for subjects < 18 years of age
 6. An acute upper or lower respiratory infection, pulmonary exacerbation, or changes in therapy (including antibiotics) for pulmonary disease within 28 days before Day 1 (first dose of study drug).
 7. Lung infection with organisms associated with a more rapid decline in pulmonary status (including, but not limited to, *Burkholderia cenocepacia*, *Burkholderia dolosa*, and *Mycobacterium abscessus*). For subjects who have had a history of a positive culture, the investigator will apply the following criteria to establish whether the subject is free of infection with such organisms:
 - The subject has not had a respiratory tract culture positive for these organisms within the 12 months before the date of informed consent.
 - The subject has had at least 2 respiratory tract cultures negative for such organisms within the 12 months before the date of informed consent, with the first and last of these separated by at least 3 months, and the most recent one within the 6 months before the date of informed consent.
 8. An acute illness not related to CF (e.g., gastroenteritis) within 14 days before the first dose of study drug (Day 1).
 9. Ongoing or prior participation in an investigational drug study (including studies investigating ELX with or without coadministration of other study drugs) within 28 days of the Screening Visit.
 - A washout period of 5 terminal half-lives of the previous investigational study drug, or 28 days, whichever is longer, must elapse before the Screening Visit.

- The duration of the elapsed time may be longer if required by local regulations.
10. Use of restricted medication (including antidiabetic medication other than insulin, which must be at a dose no greater than 0.3 units/kg/day) within specified duration before the first dose of study drug as defined in [Table 9-1](#).
 11. BMI \geq 30 kg/m² at the Screening Visit.
 12. Pregnant and breast-feeding females. All female subjects regardless of childbearing potential status (Section [11.4.6](#)) must have a negative pregnancy test at the Screening Visit and the Day 1 Visit.
 13. The subject or a close relative of the subject is the investigator or a subinvestigator, research assistant, pharmacist, study coordinator, or other staff directly involved with the conduct of the study at that site. However, an adult (aged 18 years or older) who is a relative of a study staff member may be enrolled in the study provided that:
 - the adult lives independently of and does not reside with the study staff member, and
 - the adult participates in the study at a site other than the site at which the family member is employed.

9 STUDY IMPLEMENTATION

9.1 Study Design

This is a Phase 3b, open-label study in CF subjects 12 years of age and older with F/MF genotypes and abnormal glucose tolerance ([Figure 9-1](#)). Approximately 60 subjects (F/MF genotypes) will be enrolled, of whom approximately 30 subjects will have IGT and 30 subjects will have CFRD. During the Treatment Period, subjects will be administered ELX/TEZ/IVA for approximately 48 weeks. All subjects will receive ELX 200 mg once daily (qd)/TEZ 100 mg qd/IVA 150 mg every 12 hours (q12h).

Figure 9-1 VX19-445-117 Study Design

ELX: elexacaftor; CFRD: CF-related diabetes; CGM: continuous glucose monitoring; IVA: ivacaftor; N: total sample size; TEZ: tezacaftor

^a On Day -7, a CGM sensor will be inserted subcutaneously to assess baseline blood glucose levels for 7 days prior to the first dose of study drug in subjects with CFRD.

^b Subjects who complete the visits in the Treatment Period, regardless of whether they are on a treatment interruption, will be offered the opportunity to enroll in an open-label extension safety study evaluating ELX/TEZ/IVA. The Safety Follow-up Visit is not required for subjects who complete the Week 48 Visit and have enrolled in an open-label study within 28 days after the last dose of study drug.

9.1.1 Screening

Screening Visit assessments are listed in [Table 3-1](#).

Screening will occur within 35 days before administration of study drug. The investigator (or an appropriate authorized designee) will obtain informed consent from each subject.

To prepare for study participation, subjects will be instructed on the study restrictions ([Section 9.4](#)) and concomitant medications ([Section 9.5](#)).

9.1.1.1 Repetition of Screening Assessment(s)

Screening assessments may be repeated once to establish study eligibility. If repeat values of the individual assessment(s) are within the eligibility criteria and completed within the screening window, then the subject is eligible for the study.

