9.1.1.2 Rescreening

Subjects may be rescreened once. If a subject is rescreened, the subject will provide informed consent and assent (as applicable), and all screening assessments will be repeated, except for:

- *CFTR* genotyping
- Ophthalmologic examination (if performed within 3 months before the date of informed consent)

If a subject is rescreened, a new screening window will begin when the first rescreening assessment has been initiated.

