9.1.1.3 Extension of Screening Period Window

A subject may have the Screening Period window extended by 2 weeks for the following reasons:

- Repetition of the Screening Period assessments (Section 9.1.1.1)
- Unexpected operational or logistic delays, or to meet the eligibility criteria
- Scheduling of ophthalmologic examination (Section 11.4.5)

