12.3.1 General Considerations

All individual subject data for subjects will be presented in individual subject data listings.

Continuous variables will be summarized using the following descriptive summary statistics: the number of subjects (n), mean, SD, median, minimum value (min), and maximum value (max).

Categorical variables will be summarized using counts and percentages.

Baseline value, unless specified otherwise, will be defined as the most recent non-missing measurement (scheduled or unscheduled) collected before the first dose of study drug. The baseline 2-hour blood glucose level from OGTT will be the average of measurements at screening and Day 1.

Change (absolute change) from baseline will be calculated as Post-baseline value – Baseline value.

Relative change from baseline will be calculated and expressed in percentage as 100% × (Post-baseline value – Baseline value)/Baseline value.

Treatment-emergent (TE) Period will include the time from the first dose of study drug to 28 days after the last dose of study drug or to the completion of study participation (as defined in Section 9.1.6), whichever occurs first.

Incomplete/missing data will not be imputed, unless specified otherwise.

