# 8 STATISTICAL ANALYSIS

## 8.1 General Considerations

**Continuous variables** will be summarized using the following descriptive summary statistics: the number of subjects (n), mean, SD, median, minimum value (min), and maximum value (max).

**Categorical variables** will be summarized using counts and percentages.

**Baseline value**, unless otherwise specified, will be defined as the most recent non-missing measurement (scheduled or unscheduled) collected before the first dose of study drug in the Treatment Period. The baseline 2-hour post-OGTT blood glucose level will be the average of pre-dose measurements at Screening and Day 1 visits (if both measurements are not available, use one measurement).

**Absolute change** from baseline will be calculated as post-baseline value – baseline value.

**Relative change** from baseline will be calculated as (post-baseline value – baseline value)/baseline value.

**Treatment-emergent (TE) Period** will include the time from the first dose of study drug to 28 days after the last dose of study drug or to the completion of study participation, whichever occurs first. Refer to Section 9.1.6 of the CSP for the definition of completion of study participation.

**Unscheduled visits:** Unscheduled visit measurements will be included in analysis as follows:

- 1) In scheduled visit windows per specified visit windowing rules
- 2) In the derivation of baseline and last on-treatment measurements
- 3) In the derivation of maximum and minimum values during TE period, and maximum and minimum change from baseline values during TE period for safety analyses
- 4) In individual subject data listings as appropriate

**Visit windowing rules:** The analysis visit windows for protocol-defined visits are provided in [Appendix A](#).

**Incomplete/missing data** will not be imputed, unless specified otherwise.

**Outliers:** No formal statistical analyses will be performed to detect or remedy the presence of statistical outliers, unless specified otherwise.

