  - The measurement closest to the target day will be used; or
  - If there are multiple measurements with the same distance from the target day, the latest measurement will be used. If the latest measurement cannot be determined, then unscheduled visit will be selected

 For measurements collected on the date of first dose of study drug, if it cannot be determined whether the measurement is before or after the first dose:

- Scheduled measurement will be treated as pre-dose observation.
- Unscheduled measurement will be treated as post-dose observation.

 For safety assessment, Safety Follow-up analysis visit will be based on nominal Safety Follow-up visit. If a subject doesn't have a nominal Safety Follow-up visit but has an ETT visit with study day >351, then the ETT visit will be mapped into Safety Follow-up analysis visit.

 For efficacy assessments and nutrition variables (BMI, Weight, Height and their Z-scores), if there are multiple assessments >351, then nominal Safety Follow-up visit will be mapped to Safety Follow-up visit. If there is only ETT assessment > 351, the ETT visit will be mapped to the Safety Follow-up visit; else if there are multiple assessments with >351 then select the earliest record.

Derived Variables:

- Age (in years) at first dose date and nominal visit (for demographics, listing and the calculation of [percent] predicted spirometry variables):
 

Obtain the age at informed consent (in days) in “yy, mm” format (e.g., 24 years, 6 months) from the Vital Signs (VS) page at the Screening Visit, and add 0.5 month to convert to days.

Obtain the informed consent date.

Then age (in years) at first dose or nominal visit = [(first dose date or nominal visit date – informed consent date) in days + age at informed consent (in days)]/365.25.
- Age (in months) at nominal visit (for use in calculation of BMI, height and weight z-score):
 

Obtain the age at informed consent (in months) in “yy, mm” format (e.g., 24 years, 6 months) from Vital Signs (VS) page at the Screening Visit.

Obtain the informed consent date.

Table 11-1 Analysis Visit Windows for Safety and Efficacy Assessments			
Assessment	Visit	Target Study Day	Analysis Visit Window (in study days)

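### A valid normal Screening OGTT may be repeated to qualify (at most four tests), and neither document says which Screening test then enters the primary baseline

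*Protocol*

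**What the plan says.** **Repeats.** Protocol 9.1.1.1: "Screening assessments may be repeated once to establish study eligibility". A repeat that meets the criteria inside the screening window settles the matter and admits the subject. Nothing confines this to a failed or invalid test.

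**Rescreening.** Protocol 9.1.1.2: "Subjects may be rescreened once". No reason is required. All assessments are redone except CFTR genotyping and, if recent, the eye examination, so the OGTT is redone. Section 9.1.1.3 allows a two-week extension of the window, and its reasons include "Unexpected operational or logistic delays, or to meet the eligibility criteria".

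**Entry criterion.** Inclusion 7 (Protocol 8.1) asks for "Abnormal glucose tolerance as determined by an OGTT, classified as either IGT" or CFRD. One abnormal test is enough; no confirmation is required.

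**Baseline.** Protocol 12.3.1: "The baseline 2-hour blood glucose level from OGTT will be the average of measurements at screening and Day 1". SAP 8.1: "The baseline 2-hour post-OGTT blood glucose level will be the average of pre-dose measurements at Screening and Day 1 visits", using one value if the other is unavailable. Appendix A note 6 repeats this. Non-fasting OGTTs are set to missing (SAP 8.3.1.1). No text says which Screening OGTT is averaged when there is more than one.

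**The concern.** Protocol 9.3.1 justifies two baseline OGTTs by the known variability of the test. The repeat rule works against that protection. A subject whose usual 2-hour glucose lies somewhat below 140 mg/dL can qualify on a chance high reading. If only that reading is carried into the baseline, the test that showed the usual level is lost.

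The later return to the subject's own level then counts as a fall from baseline. There is no control arm to absorb it, because the primary hypothesis is a mean change of zero. The objective also concerns subjects with IGT or CFRD, and retesting admits more subjects whose usual value is in the normal range.

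**Working it through.** **1. The plan's own figure.** Inputs from Protocol 12.1: N = 60, 10% dropout (54 evaluable), change -30, SD 45 mg/dL, two-sided 0.05, one-sample t-test. Noncentrality = (30/45) × √54 = 4.90, and the exact noncentral t gives power 0.998. The stated figure of more than 95% is reproduced.

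**2. Number of tests.** One test plus one repeat, then one rescreening with one repeat: 2 × 2 = 4 at most.

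**3. Chance that a truly normal subject qualifies.** The documents give no within-subject SD, so 20, 30 and 40 mg/dL are assumed. Take a true 2-hour value of 125 mg/dL, a threshold of 140, and ignore the fasting criterion. Then p = P(Z > 15/SD), and the chance of at least one qualifying result in k tests is 1 - (1 - p)^k. At SD 30, p = 0.309, and 1 - 0.691² = 0.52.

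| Within-subject SD | 1 test | 2 tests | 4 tests |
|---|---|---|---|
| 20 | 23% | 40% | 64% |
| 30 | 31% | 52% | 77% |
| 40 | 35% | 58% | 83% |

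**4. Spurious change with no drug effect.** Simulation, with these assumptions:
- true 2-hour values normal with mean 150 or 170 and between-subject SD 50;
- independent test error with the SD shown;
- entry at 140 or above, with equal IGT and CFRD groups by the qualifying test;
- outcome = mean of Weeks 36 and 48.

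Columns A and B use baseline = (qualifying Screening + Day 1)/2. Column C averages all pre-dose tests. In B and C every normal first test is repeated once, which is an upper bound. Units are mg/dL; simulation error is about 0.1.

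| Mean, SD | A: no repeats | B: one repeat | B minus A | C: all tests averaged |
|---|---|---|---|---|
| 150, 20 | -3.4 | -4.0 | -0.6 | -3.2 |
| 150, 30 | -6.7 | -8.0 | -1.3 | -6.1 |
| 150, 40 | -10.3 | -12.2 | -1.9 | -8.8 |
| 170, 20 | -2.2 | -2.8 | -0.6 | -2.1 |
| 170, 30 | -4.5 | -5.6 | -1.1 | -4.0 |
| 170, 40 | -7.0 | -8.7 | -1.7 | -5.9 |

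If a quarter of normal tests are repeated, the added part is 0.2 to 0.6. With universal repeating, 7 to 18% of subjects enter by repeat.

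**5. Where it sits.** Among repeat-qualifiers alone (separate summary without the equal-group quota) the spurious change is about -8 to -16 mg/dL across the six scenarios. At mean 150, SD 30 it is -12, against +1 when all pre-dose tests are averaged; about 46% of these subjects have a true value below 140.

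**6. Effect on the test.** At n = 54 and SD 45, a spurious shift of 6 mg/dL gives rejection 16% of the time and a shift of 8 gives 25%, against a nominal 5%. At mean 150, SD 30 these are close to columns C and B. The baseline covariate in the MMRM does not remove the shift, because with complete data the LS mean at the average baseline equals the observed mean change.

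**The case against.** Several stronger readings are tempting, and the documents do not support them.

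- **Testing continues until a result is abnormal.** It is capped at four tests, and the last two need fresh consent and almost all of screening again. Nothing shows that sites would go that far.
- **The baseline is the qualifying value alone.** It is averaged with Day 1, which is not used for selection, and this halves the selection effect. The qualifying value stands alone only when the Day 1 test is missing or non-fasting.
- **The SAP instructs that the normal test be discarded.** Appendix A note 2 says "The measurement closest to the target day will be used", but the OGTT has a single Baseline window with target Day 1. Applied literally, the rule would drop every Screening value and contradict the stated average, so note 6 must govern. SAP 8.1 also admits unscheduled measurements into the derivation of baseline. The choice is therefore unspecified.
- **The whole null change is due to repeats.** Columns A and B show that about 80 to 85% of it remains with no repeats in most scenarios; it comes from putting a selecting test into the baseline at all.

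The secondary endpoint is largely protected: its baseline category is the most recent pre-dose result, normally Day 1, and subjects who are normal then leave the denominator (SAP 8.3.2.2).

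These objections limit the size of the point. They do not answer the missing rule: a derivation of the primary endpoint is open, and one natural way to fill the gap adds bias.

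**Conclusion.** The point holds in limited form. A valid normal OGTT may be repeated, one abnormal result admits the subject, and the plan does not say which Screening OGTT is averaged. If it is the qualifying one, one repeat adds about 0.6 to 1.9 mg/dL of spurious decrease when every normal test is repeated, or 0.2 to 0.6 when a quarter are. This is small against the planned 30 mg/dL, but it falls on a minority of subjects and comes on top of the 2.2 to 10.3 mg/dL from selection on Screening.

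The figures rest on assumed within-subject SDs of 20 to 40, population means of 150 or 170, between-subject SD 50, and unknown repeat rates. The case for change is that it costs little and settles the primary baseline before database lock.

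**What to change.** **SAP 8.1 and Appendix A note 6.** Define the baseline 2-hour glucose as the mean of all valid fasting pre-dose OGTTs from Screening through Day 1. Include a valid test that did not meet inclusion 7, and a test from the earlier screening where it was captured. List this in SAP 2.1, which now records no modification, as a change from Protocol 12.3.1.

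**Reporting.** Give the number of subjects who qualified on a repeat or rescreen. Add a sensitivity analysis with Day 1 alone as baseline; its expected change with no drug effect is about zero, so it also addresses the larger bias from selecting on Screening.

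**Cost.** A few SAP sentences and no new procedures. Subjects will contribute different numbers of baseline tests. OGTTs from a failed first screening may not be in the database: Protocol 13.3 requires screening results for enrolled subjects but does not say whether a previous failed screening is kept.

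**Optional.** Restrict OGTT repeats in Protocol 9.1.1.1 to invalid tests. This costs some screen failures and would not remove the larger bias in column A.
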